ProSPECT - Protocol Submission Portal and Electronic Communication Tracker

Date: Wednesday, April 21, 2021 10:51:23 AM

Print Close

ID: Pro00003161

View: 0.0 Type of Submission Entry

Study Identification Information

This is the first step in your Human Research Application. You will automatically be guided to the appropriate forms needed to complete your submissions.

1.0 * Study Name:

Neurophysiological and Kinematic Predictors of Response in Chronic Stroke (SRT5)

2.0 * Brief Description (using layman's terms) - 500 words or less:

Stroke is the leading cause of neurological disability in the veteran population and upper extremity dysfunction is a major cause of functional loss. The costs of rehabilitation are significant and practically limits therapy to the first few months after stroke onset. Recent results show clearly that patients with chronic stroke benefit from rehabilitation and robot assisted therapy offers a more cost effective approach to this patient group. In this study, we are validating a predictive model that uses demographics, functional status, genomics, neurophysiology, neuroanatomy, and other potential biomarkers to predict the likelihood of a clinically significant change in impairment at the end of a robot assisted therapy intervention.

3.0 * Is this research study a Greater than Minimal Risk Clinical Trial? Yes No**4.0 * Is this study a Greater than Minimal Risk Comparative Effectiveness research?** Yes No**5.0 * Principal Investigator:**[[name]](#)**5.1 * VA hours per week the PI is devoted to project:**

10

5.2 * Is the PI working with ionizing radiation? Yes No**5.3 * Is the PI working with biological hazards?** Yes No**5.4 * Is the PI shipping biological hazards?** Yes No

A completed and signed Research Financial Conflict of Interest Statement is required for all investigators (including Principal Investigators, Co-Principal Investigators, and Co-Investigators) listed on the study application. **Financial Conflict of Interest Form-Nov. 2013**

 Other VA Resources: VA Equipment
 Other VA Resources: VA Property (Including space leased to, or used by VA)
 Other VA Resources: VA Databases
 None of the Above apply to this research

ID: Pro00003161

View: 1.3 Study Funding Information

Study Funding Information

1.0 * Funding Sources:

Funding Source	(Other)	Code
View Merit Review (CC 103)		9003

2.0 Upload Grant Application, if applicable (If NIH, VA, voluntary agency, must upload):

Name	Modified Date
Grant Application	7/12/2019 1:45 PM

ID: Pro00003161

View: 1.4 Resources

1.0 * Do you currently have adequate resources (e.g., staff, physical space, information technology, etc.) to protect the safety of participants, staff, and the confidentiality of subjects' data during the conduct of this study?

Yes No

If yes, include a listing of the VAPHS resources that will be used for this study and are necessary to protect participants.

The main laboratory area is the Laboratory for Research on Arm Function and Therapy (RAFT) which is located in the Keystone building, a commercial building leased by the University of Pittsburgh, with a pending Memorandum of Understanding regarding its use as VA Research Space. There is an off-site waiver for the current study-related activities in RAFT, which is part of the Rehab Neural Engineering Labs (RNEL.) The laboratory contains a variety of devices designed around upper extremity motor function. This includes transcranial magnetic stimulation (TMS) equipment (a rapid stimulator capable of modulating brain activity for several minutes, standard TMS stimulators and Bistim device), and Brainsight Neuronavigation systems. There is a unimanual exoskeleton robot (Armeo Power) and a bimanual KINARM exoskeleton robotic system (B-Kin / KINARM, Kingston, ON.)

University Drive VAPHS: All veterans will have their functional evaluations in the occupational therapy area at this facility.

Human Engineering Research Laboratories (HERL) are a part of the U.S. Department of Veterans Affairs as the Center for Wheelchairs and Associated Rehabilitation Engineering. [name] has office space in this facility and receives administrative and scientific support from its faculty and staff. Sensitive data will be stored within its VA resources.

If no, please describe the resources that will be needed and explain how the resources will be obtained before the study is initiated:

2.0 * VAPHS requires that either the PI or co-PI have a *physical presence* at VAPHS. Please describe the role the PI and/or co-PI have at VAPHS with respect to clinical responsibilities or in relation to other research activities.

The P.I. is a 5/8 part-time employee of VAPHS, with an appointment as Neurologist in the Medicine Service. He has 2/8 of clinical effort, which is on the Outpatient Neurology service, seeing consultations and follow-up patients preferentially with stroke and movement disorders, as well as other general neurological disorders. The remainder of his effort is devoted to VA specific research.

3.0 * Will off-site ancillary service facilities (e.g., radiology services, central labs, non VA space, etc) be used for this study?

Yes No

If yes, please provide the location and a brief description of the project activities to be conducted at the off-site ancillary facilities:

MRI scans will be conducted at the Magnetic Resonance Research Center, which houses and operates two 3T Siemens Prisma systems and has research staff and technologists to support our project.

The Main Laboratory Area is the Laboratory for Research on Arm Function and Therapy (RAFT) part of the Rehab Neural Engineering Labs (RNEL.) The laboratory is in the Keystone Building,

second floor, in one suite that contains a variety of devices designed around upper extremity motor function. This includes transcranial magnetic stimulation (TMS) equipment (a rapid stimulator capable of modulating brain activity for several minutes, standard TMS stimulators and Bistim device), Brainsight Neuronavigation systems. There is a bimanual KINARM exoskeleton robotic system (B-Kin, Kingston, ON.).

4.0 * Will a firm be contracted to obtain consent from subjects, collect private individually identifiable information from human subjects, or be involved in activities that would institutionally engage the firm in human subjects' research?

Yes **No**

If yes, please provide a description of the contracted service(s):

* Please specify the IRB that has oversight of the firm's activity(ies):

Name of Site / Institution	IRB Approval Document	FWA Number
There are no items to display		

5.0 Collaborations

Please list any non-VAPHS institutions or individuals (i.e. co-authors, mentors, etc.) that you will collaborate with and describe their specific role in the research:

[name] will supervise the clinical evaluations of upper extremity function and TMS studies. As Assistant Professor in the Department of Occupational Therapy at the University of Pittsburgh, he is a clinical investigator who is experienced in the assessment of upper extremity function and the training of stroke survivors in upper extremity functional use.

[name] specific role is designing acquisition and analysis methods for the MRI portion of the proposed work. He is an Assistant Professor in the departments of Radiology and Bioengineering at the University of Pittsburgh. Research interests include brain perfusion modeling, cerebrovascular regulation mechanisms, and technical development and quantification of functional MRI, all relevant for this study.

5.1 If this is not Multi-Site Research, please upload the appropriate written agreement(s) here:

Name

There are no items to display

ID: Pro00003161

View: 1.5 Project Information

1.0 Does the project involve any of the following (check all that apply):

Type

- Biological Hazards (including human biological specimens)
- Chemicals
- Ionizing radiation or use of radioactive materials
- Drug, Biological, or Nutritional (e.g. herbal or dietary) Supplement

2.0 Project Focus (check if applicable):

Type

- Traumatic Brain Injury (TBI)
- Post Traumatic/Post Deployment Stress Disorder (PTSD/PDSD)
- Operation Iraqi Freedom/Operation Enduring Freedom (OIF/OEF)

3.0**KEYWORDS**

Please provide a minimum of 3, maximum of 6 keywords. Please use MeSH terms.

- * stroke
- * rehabilitation
- * robotics

4.0 * Please describe the type of study:

one-arm, multiple baseline sequential, cohort study

5.0 * Will any of the research being conducted as a part of this study be used to fulfill academic requirements (e.g., master's thesis, dissertation, or other academic program requirements necessary to obtain a degree/certification, etc.)? Yes No

ID: Pro00003161

View: 1.6 (CR) Study Locations

Study Locations

1.0 * Please add the local sites where this study will be conducted:

Location

[View](#) VAPHS University Drive Division

[View](#) Other

If Other, Please Specify:

The Laboratory for Research on Arm Function and Therapy (RAFT).

The Human Engineering Research Laboratories (HERL), part of the U.S. Department of Veterans Affairs as the Center for Wheelchairs and Associated Rehabilitation Engineering.

ID: Pro00003161

View: 1.6.1 (CR) Multi-Site Study

1.6.1 Multi-Site Study

1.0 * Is this a multi-site study:

Yes No

ID: Pro00003161

View: 1.6.1.1 (CR) Multi-Site Study

1.6.1.1 Type of Multi-Site Research

1.0 * Type of Multi-Site Research:

Research NOT Conducted Under a Cooperative Research and Development Agreement (CRADA) with a Pharmaceutical Company or other Non-Federal Entity ("Collaborative Research").

ID: Pro00003161 View: 1.6.1.1.2 (CR) Multi-Site Not Conducted Under CRADA

1.6.1.1.2 Multi-Site Not Conducted Under CRADA

1.0

*** Status of the PI in Proposal (check all that apply):**

Coordinating Investigator in multi-site study (includes studies conducted both at VAPHS and Pitt)

Provide Further Details (if needed):

ID: Pro00003161 View: 1.6.1.1.2.1 (CR) Coordinating Investigator

1.6.1.1.2.1 Coordinating Investigator

1.0 * Number of currently participating institutions/sites (including VAPHS and international sites, if applicable):

2

2.0 * Does this study involve international/transnational research?

Yes No

Please answer the questions below for all research conducted within the United States, its territories, or Commonwealth:

3.0 * Specify other research sites where this research will be conducted:

Name of Site / Institution

IRB Approval Document

[University of Pittsburgh](#)

4.0 Provide details with regards to coordinating center responsibilities:

As both sites in the study are the RAFT Lab and the research is being overseen by identical study staff, once the VA protocol is approved, the University of Pittsburgh protocol will be modified to reflect the coordinating site protocol. The study coordinator will ensure that all study documents and amendments are performed to reflect the coordinating site. The PI and study coordinator will assure that the University of Pittsburgh will safeguard VA data as required by VA information security policies. The study coordinator will communicate to engaged participating sites SAEs that have the potential to affect of the study and study events and interim results (if appropriate). The study coordinator and PI will report all non-compliance with the study protocol or applicable requirements is reported in accordance with VHA Handbook 1058.01.

5.0 Please upload the study-wide sample informed consent form(s), protocol, and another other relevant documents, as applicable.

Name

There are no items to display

6.0 Upload applicable agreement(s) with non-VA collaborators (e.g., Research Data Use Agreement) that address such issues as the responsibilities of each party, the ownership of the data, and the reuse of the data for other research and any other relevant documents.

Name

[VA MRI contract](#)

[RDUA with MRRC](#)

Provide further details (if necessary):

ID: Pro00003161

View: 1.7 Section Chief and Service Line VP approvals

Please upload the approval of the Section Chief, if applicable and the Service Line VP.

- 1.0 * Institutional Approval Document:**
[Institutional Approval Document\(0.02\)](#)

ID: Pro00003161

View: 2 Study Objectives & Design

Study Summary**1.0 Funding End Date:****2.0 * Abstract. Please provide a brief description of the study.**

Stroke is the leading cause of neurological disability in the veteran population and problems with arm movement are a major cause of loss of functional ability. The costs of rehabilitation are significant and effectively limit therapy to the first few months after stroke onset. Recent results show clearly that patients with chronic stroke (> 6 months) benefit from intensive arm practice. Robot assisted therapy followed by task related training offers a cost-effective approach to this type of practice that also results in better arm function in daily life. A previous study has shown that it is possible to predict who will benefit from this kind of treatment, specifically what individual characteristics are related to a clinically meaningful improvement in arm movement. This next phase of the study will test whether the prediction method is reproducible and independent of the type of robot being used. It will also expand knowledge of how the brain area most important for movement changes its connections with other brain areas and the muscles in the arm.

3.0 * Describe the study objectives. Please include primary aim and hypothesis, if applicable any secondary aims and hypotheses.

Chronic upper extremity dysfunction after stroke is a leading cause of disability and has been the target of many therapeutic methods that involve repetitive task practice. Clinical trials of intensive practice-based interventions have demonstrated significant changes in mean impairment in a group, but variable effects among individuals, with clinically significant improvements in only a fraction of the population. This is true of our previous Merit Review study, which showed good mean gains in several areas, and about half of participants having clinically significant changes in the primary outcome of motor impairment. The basis for these variable responses is not known, i.e. we do not know the biological mechanisms that moderate response to these standardized interventions. And while recovery of function is associated with normalization of brain network interactions and task-related brain activation, the causal role of these changes is not well understood. In our current project period, we are continuing to address both issues with construction of a predictive model that uses demographics, functional status, genomics, neurophysiology, neuroanatomy, and other potential biomarkers to predict the likelihood of a clinically significant change in impairment at the end of the intervention.

Our long-range goal is the prescriptive application of intensive task practice to veterans who have suffered a stroke, maximizing the cost-benefit ratio. We therefore plan to externally validate the predictive value of biomarkers as incorporated in the model resulting from our previous chronic stroke robotic rehabilitation trial. We will not only validate the predictive model in a new cohort, we will now quantify the *changes* in functional connectivity of the affected hemisphere's primary motor cortex with other brain areas and with the spinal cord, in order to uncover the mechanisms by which intensive task practice leads to increased motor ability. We will continue to use an effective intervention for individuals with chronic stroke, robotic training

with transition to task practice (Robot + TTT,) now focusing on use of an *exoskeleton platform*, which has already been part of our intervention. We propose the following two specific aims in the proposed renewal of this award:

1. To validate a predictive model based on baseline measures of biological and functional biomarkers. *Working hypothesis: Baseline factors that include functional and physiological status will predict clinically significant responses to therapy.* Change from use of end-effector and exoskeleton robots to solely exoskeleton will not significantly affect the prediction model. The rationale for the hypothesis is that the effects of assisted repetitive task practice is not dependent on a particular technology but does depend on a biological substrate. Expected outcomes: The predictive model will be externally validated, a receiver operating curve described, and the intervention and model validated on an exoskeleton platform for delivering therapy.

2. To identify the changes in the input and output of the affected primary motor cortex associated with change in motor impairment. *Working hypothesis: Increased input into the motor cortex, increased output from the motor cortex, or both, underlies the treatment effect of repetitive task practice.* Normalization (increase) in connectivity of affected primary motor cortex to other motor brain areas of both sides of the brain will be associated with reduction of motor impairment. In a subpopulation of treatment responders an increased effectiveness of the motor cortex in directly activating muscles will be demonstrated. Expected outcome: The causal role of task practice in changing a brain region's connectivity will be known, with potential uses as a surrogate measure of outcome in rehabilitation trials. Resting state BOLD MRI, transcranial magnetic stimulation, and clinical electrophysiology will be used to provide data regarding the mechanisms of training-related gains.

When we have completed the above aims, we will have a validated algorithm by which a set of baseline variables (biomarkers) can be used to inform both the clinician and patient regarding the likelihood of successful training, in an appealing exoskeleton robotic rehabilitation platform, for upper extremity disability in the chronic period after stroke. This algorithm can be modified to consider those biomarkers that are more practical in VA clinical settings. We will also extend mechanistic knowledge about the response to intensive training on brain connectivity, which has been noted to be altered after stroke and which may relate to learned non-use of the affected limb and loss of spinal response to descending input. We will have new efficacy data on the use of assisted mass practice followed by assisted task practice on multiple dimensions of functioning and disability, including use of the arms in daily life.

4.0 * Provide a summary of the background of the study, and explain how this research will contribute to existing knowledge. Describe previous studies that provides a basis to show that the proposed research can be carried out without undue risk to human subjects.

Stroke is the leading cause of long-term disability [1] costing an estimated \$38.6 billion a year [2] and stroke-related disability is becoming more prevalent [3], even as overall rate of stroke is in slight decline. Recent evidence indicates that the brain can remodel after stroke, even years later, through neuroplasticity (including changes in excitability and synaptic strength) and synaptogenesis [4-6]. Behavioral remodeling also occurs and allows compensatory movement patterns to accomplish

task goals [7-9]. Interventions incorporating strategies of task specificity, challenge, and repetition appear to be key factors in promoting these two types of remodeling and are central elements in rehabilitation of motor weakness following stroke [11]. Since our initial project period, the value of robot-assisted therapy to improve upper extremity function has become more established but there are still questions about many aspects of implementation, including patient selection, dose, and type of treatment [12]. There are two basic types of rehabilitation robots, *endeffector*, in which the patient engages with the tip of the limb, and *exoskeleton*, in which a powered framework encloses the limb. Both types have demonstrated efficacy [13] with some potential advantage in full use of exoskeleton capabilities in training joint coordination [14], and we have used both types in our ongoing study. Robot-assisted and other types of upper extremity treatment studies in chronic stroke report relatively modest *average* gains in motor function that typically fail to translate into meaningful change in everyday use of the paretic arm [15]. This has prompted us to directly address issues of predicting response, promoting and measuring translation to daily use and determining optimal scheduling for that therapy. Therefore, there is now a critical need for research that: 1. predicts response to hybrid robotic and functional task oriented therapies in chronic stroke and 2. determines the brain mechanisms of response to such therapies so that we better understand why such therapies work for some, but not all, stroke survivors.

5.0 * Describe the overall significance of the research in terms of the problem to be studied and potential findings, as well as its relevance to the care of veterans, the VAPHS, and the VHA:

Importance and Impact

The primary purpose of the current proposal is to externally validate predictors of response to Robot + TTT (transition-to-task) therapy in the chronic stroke population. By doing so, we will validate biomarkers and algorithms for a predictive model to guide matching of patients to a therapy based on residual neural and motor function and other measurable factors. We have been contributing to understanding the mechanisms of recovery specifically by relating baseline clinical, neurophysiological and kinematic markers to functional outcomes. We are now proposing to go beyond this contribution by measuring specific changes in connectivity of the primary motor cortex, the hub of voluntary movement function in the human brain.

While we, and others, have as a goal personalized treatment during the *sub-acute* period when spontaneous recovery, optimal neuroplasticity and available rehabilitation coincide, the field has been turning to **chronic** populations for a few reasons. First, doing so addresses the problem of an exponential growth in individuals aging with disabilities from stroke. Strokes are occurring earlier in the lifespan [16] and individuals live longer with stroke [17] therefore causing increased costs to society as a public health concern as well as increased costs to the individuals who face more years with a lower quality of life. Since it is known that neuroplasticity continues across the lifespan [18] and that rehabilitation can be effective years after the stroke e.g. [19], validating biomarkers and algorithms that *best match individuals with a specific therapy will maximize recovery of function and reduce health care resource utilization over the long term. Second, providing further evidence*

for optimal use of robotic therapy in the chronic period may provide an impetus for the installation of robots and other arm exercise programs into health clubs and veteran's service organizations where rehabilitation and exercise can usefully combine.

Impact on Health Care Delivery for Veterans:

The long-range goal of the proposed work is to meet the Department of Veterans Affairs Strategic Plan 2014-2020 listed objective 1.1 and create evidence-based rehabilitation methods for veterans with stroke related upper extremity hemiparesis that focus resources more efficiently. Prevalence of stroke-induced disability in our veteran population is expected to rise since 64% of the population is aged 55 or older [20]. Robotic devices provide a cost-effective method to automate parts of therapeutic practice, allowing more efficient use of therapist time while providing high doses of training [21]. We expect that the results from this study will validate and possibly refine our method for choosing the Robot + TTT rehabilitation technique during the long period following sub-acute recovery. It will also bring insights for the science of predicting outcomes and optimally matching therapeutic techniques in this period. While use of robotic training is a key part of the treatment in this trial, we take steps toward generalization with the use of an advanced robotic rehabilitation system piloted in the current study. Inclusion of an exoskeleton robot is also in line with the RR&D service's call for studies of such devices.

6.0 Please upload any additional documents:

Name	Version
There are no items to display	

ID: Pro00003161

View: 2.1 Required Reviews

Required Reviews

1.0

Type of Submission:

New study

If this is a 'New Paper Conversion' please include the MIRB Number:

Please upload a letter certifying that you have made no modifications or amendments in converting this research study from paper to electronic:

2.0

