Transcranial magnetic stimulation of the motor cortex is performed using a MagStim 200 Magnetic Stimulator (MagStim Ltd., Wales, UK) to assess changes in brain physiology and MEP in arm muscles. Surface electromyography (B&L Engineering, Santa Ana, CA) is used to record muscle activity from three muscles (first dorsal interosseous [FDI], extensor carpi radialis [ECR], the anterior deltoid [AD]) on both the paretic and non-paretic arms. SIGNAL (CED, Oxford, UK) scripts are used to drive single pulse TMS and collect simultaneous EMG data through a Power 1401 (CED) system. TMS sessions are completed at three time points: baseline, post-training, and at the 12-week follow-up visit. Soft foam earplugs are inserted into each ear canal for hearing protection.

Prior to the initial TMS session, a skin and whole-brain reconstruction are created from the participant's high resolution anatomical MRI scan, using neuronavigation software (BrainSight, Rogue Research, Montréal, QC, Canada). The hand knob in each hemisphere is identified from the anatomical scan and used as the center point for hotspot grid (described below). The neuronavigation software records three-dimensional coordinates of each TMS stimulation site, measured using an optical digitizing device (Vicra, Northern Digital Inc.). Thus, this technique ensures reproducible locations at each session.

MRI Evaluation:

Participants will lay down and be positioned in the scanner by MRRC staff with supervision from study staff. They will be given a device to communicate any discomfort to staff and the procedure can be paused or discontinued at any time. The MRI procedure will take approximately 1.5 hours. The MRI facility is located at the UPMC MR Research Center. It consists of two 3T Siemens Prisma scanners.

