The primary analysis will be correlation between change in physiological parameters (e.g. affected M1 connectivity, recruitment curve slope) and change in FMA. Analysis of H-reflex changes will be compared to recruitment curve changes to rule out a general change in lower motor neuron excitability. Secondly, there will be correlations of these parameters at baseline with baseline motor function measures. A more detailed analysis of the MRI data will also examine individual interregional connections to determine whether any of them are more sensitive to the intervention than others. There will be exploration of whether the predictive model also predicts changes in physiological measures, which could lead to more efficient studies in the future.

ID: Pro00003161

View: 5 Sub-Studies

- 1.0** *** Is there a sub-study or are there sub-studies associated with this study?**
There is no sub-study associated with this study.

ID: Pro00003161

View: 6 Study Population Summary

Study Population Summary

1.0 * What is the maximum number of subjects you plan to enroll at VAPHS?
80

2.0 * Do you plan on enrolling patients into different categories:
 Yes No

If yes, please explain:

3.0 If this is a multi-site study, indicate the projected total subject accrual:
70

4.0 * Please provide a justification for the sample size:

Based on our record of recruitment and design feasibility, we propose to enroll 64 participants. Our current 12-week study has an attrition rate after enrollment of 12% so we anticipate completing about 57. We verify that with our sample size of 57, we will be able to estimate the area under the Receiver operating characteristic (ROC) curve (AUC) with an adequate precision (that is, the standard error is reasonably small). The AUC is an important measure to describe the performance of a predictive model for a binary outcome such as the change in FMA of greater than 4. The table below displays the standard error (SE) of the estimated AUC for several values of the true AUC and different prevalence of responders [10]. The SE is less than 0.07 in all cases except when AUC is 0.7 and the proportion of responders is only 33%. (This is the current situation in the preliminary analysis, providing an upper bound on our AUC measure.)

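### Aim 2 credits FMA-related change to the affected motor cortex, but no planned analysis uses the unaffected side as a within-person comparator

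*Combined protocol and SAP*

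**What the plan says.** The study is described in View 1.5 as a "one-arm, multiple baseline sequential, cohort study". Specific Aim 2 (View 2, item 3.0) concerns the affected primary motor cortex. It predicts that "Normalization (increase) in connectivity of affected primary motor cortex to other motor brain areas of both sides of the brain" will accompany a fall in motor impairment, and states as its expected outcome: "The causal role of task practice in changing a brain region's connectivity will be known". The closing paragraph of that item speaks of "brain connectivity, which has been noted to be altered after stroke", but gives no normal value and no reference group.

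View 4.1, Analysis Plan for Aim #2, states: "The primary analysis will be correlation between change in physiological parameters (e.g. affected M1 connectivity, recruitment curve slope) and change in FMA". One specificity check follows: "Analysis of H-reflex changes will be compared to recruitment curve changes to rule out a general change in lower motor neuron excitability". Individual interregional connections will also be compared for their sensitivity to the intervention.

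The data already reach both sides. In View 4, TMS Outcomes, the hand knob is located in each hemisphere and surface EMG is recorded "on both the paretic and non-paretic arms". The MRI section correlates an M1 arm-area seed, side not stated, with the rest of the brain, and takes internal-capsule FA on each side. TMS and MRI are each done once at baseline, once after training and once at the 12-week follow-up, in participants eligible for them.

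**The concern.** The claim is about one cortical area, but the planned correlation by itself cannot tell change confined to the affected M1 from change in both hemispheres. Head motion, arousal or global BOLD signal can differ between a participant's two sessions and move the connectivity scores of both hemispheres together. If that shift also runs with clinical improvement, for instance if better improvers lie stiller in the later scan, it yields a correlation between "affected M1 connectivity, recruitment curve slope" and FMA change with no affected-specific process behind it.

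There is no control group and no repeat baseline scan to show how much these measures move without treatment. At stake is the mechanistic reading of Aim 2: whether an association can be credited to the affected M1 and offered as a surrogate outcome. Aim 1 is not touched.

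Separately, the plan equates normalization with increase. Without a reference level, any rise qualifies, whatever the starting value.

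**Working it through.** **The plan's own figure.** View 6, item 4.0 gives a detectable correlation of 0.365 for n = 57, alpha 0.05, beta 0.2. By Fisher's z, two-sided: r = tanh[(1.960 + 0.842)/√(57 − 3)] = tanh(2.8016/7.348) = 0.364. Power at r = 0.365 is 80.3%. The figure reproduces and is not in dispute.

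**What serves as a comparator.**
- Unaffected-hemisphere areas are connectivity targets. A global shift raises affected-to-unaffected connectivity too, so they do not control for it.
- The H-reflex comparison addresses lower motor neuron excitability on the TMS output side. It says nothing about the MRI measure.
- FA on each side is a structural measure, not a comparator for change in functional connectivity.
- No unaffected-M1 seed, non-paretic recruitment curve or side-to-side contrast is named.

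**Model.** Let F be FMA change and g a session-wide component with corr(g, F) = ρ. Affected- and unaffected-side changes are A = √w·g + √(1 − w)·e₁ and U = √w·g + √(1 − w)·e₂. The errors are independent of each other and of F, so no affected-specific effect exists. The documents give neither w nor ρ; both are assumed. Then:
- corr(A, F) = ρ√w
- corr(A − U, F) = 0, because the two sides load equally on g
- partial corr(A, F given U), with a = √w and b = ρ, is ab(1 − a²)/√[(1 − a⁴)(1 − a²b²)]

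Share of 10,000 simulated trials of n = 57 with a significant result (two-sided 5%):

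| ρ | w | corr(A, F) | A only | A adjusted for U | A − U |
|---|---|---|---|---|---|
| 0.3 | 0.25 | 0.15 | 20% | 14% | 5% |
| 0.3 | 0.50 | 0.21 | 36% | 15% | 5% |
| 0.3 | 0.75 | 0.26 | 50% | 12% | 5% |
| 0.5 | 0.25 | 0.25 | 47% | 31% | 5% |
| 0.5 | 0.50 | 0.35 | 79% | 37% | 5% |
| 0.5 | 0.75 | 0.43 | 93% | 27% | 5% |

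At ρ = 0 all three columns are about 5% for every w. Adding the same constant to every participant's change leaves the result identical (4.9% with and without it).

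**Why covariate adjustment is not enough.**
- a = 0.5, b = 0.3: 0.15 × 0.75/√(0.9375 × 0.9775) = 0.12, or 78% of the spurious 0.15.
- a = 0.7, b = 0.5: 0.35 × 0.51/√(0.7599 × 0.8775) = 0.22, or 62% of the spurious 0.35.

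**Price of the difference score.** Suppose the true affected-side correlation is 0.365 and the session component is unrelated to F. Then corr(A − U, F) = 0.365/√[2(1 − w)], which is 0.258, 0.298, 0.365 and 0.516 at w = 0, 0.25, 0.5 and 0.75. Simulated power is 50%, 63%, 81% and 99%, against about 80 to 81% for A alone.

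**The case against.** A reader might infer that the plan ignores the unaffected side altogether. It does not: motor areas on both sides are targets, FA is bilateral, the interregional analysis could include unaffected-side pairs, and the parameters in View 4.1 are given only as examples. What is missing is any stated use of that side as a comparator.

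A reader might also infer that any session-wide shift would be mistaken for recovery. That is not so for a correlation of changes. A shift common to everyone cancels, and one unrelated to FMA change only adds noise. Bias needs a session factor that tracks improvement, and nothing in the documents shows that one exists or how strong it would be.

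Further objections stand in part. The unaffected M1 is an imperfect control because stroke or training may change it too. The two whole-brain seed scores share the M1-to-M1 connection, and Aim 2 itself predicts a rise in connectivity to both sides, so subtraction can remove real signal. Nor is the unaffected side the only possible safeguard: head motion can be estimated from each scan and adjusted for directly. These points argue for a sensitivity analysis rather than a new primary analysis. They do not supply the missing comparison.

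Finally, *normalization* may be called mere wording, since the plan glosses it as increase and specifies no test of it. That is why the remedy is only a change of word. The unaffected M1 after stroke is not a normative reference, so movement toward it would not justify the term either.

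**Conclusion.** The point holds in a limited form. As planned, an Aim 2 association cannot be assigned to the affected M1 rather than to a bilateral or global shift, because no within-person comparator is specified and the H-reflex check covers one output-side explanation only. The planned correlation is not shown to be biased; it is exposed to bias if a participant-specific session factor tracks FMA change.

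The 20% to 93% range rests wholly on the assumed w and ρ, on equal loading of the two sides and on n = 57. It illustrates what could happen and is not an estimate for this trial. That the plan gives no reference for normalization needs no assumption.

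**What to change.** In View 4.1, Analysis Plan for Aim #2:

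1. Keep the affected-side correlation with FMA change as the primary analysis.
2. From the existing scans, compute the same seed score for the unaffected M1. For this comparison, leave the M1-to-M1 connection out of both scores. Compute the non-paretic recruitment slope where it was recorded.
3. Report the correlation of unaffected-side change with FMA change in parallel, and that of affected-minus-unaffected change with FMA change as a sensitivity analysis. Do not rely on covariate adjustment alone.
4. Claim an affected-M1-specific effect only if these results support it; otherwise describe the association without that attribution.
5. In View 2, item 3.0, write *increase* instead of *normalization*.

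The cost is a little extra analysis on data already planned, with no new visits or scans. The difference score loses power when less than half the variance is shared (about 50% to 63% at shares of 0 to 0.25), and it may subtract real change on the unaffected side. It should therefore stay a sensitivity analysis, and a null result from it should not be read as evidence against an affected-side effect.
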